### **8.11.5 Length of hospital stay**

Length of Hospital Stay is defined as the difference of date of discharge and date of completing the ablation procedure. Descriptive summary statistics of the length of stay will be presented for the initial ablation and re-ablations.

### **8.11.6 Re-admission rate**

The Re-admission Rate is defined as the percentage of subjects with any re-admission to the hospital within 30 days post-ablation (including the original ablation or a repeat ablation). The number and percentage of subjects with re-admissions will be summarized, along with the reasons for re-admission.

Listings will be provided for those with any re-admission.

## **8.12 Plans for Interim Analysis**

No interim analyses are planned for the purpose of stopping the study early for success or futility.

An interim analysis for study sample size re-estimation per the observed Technical Efficacy Rate will be performed after 50% of the target enrolled subjects complete the Visit 3 (at least  $n_1=54$  evaluable subjects with primary effectiveness endpoint data). To warrant the originally intended 80% power of the study at the 0.025 level (1-sided), the sample size may be increased to a maximum of 200 enrolled subjects in order to provide 180 evaluable subjects, given the expected dropout rate.

The sample size re-estimation method is based on evaluation of conditional power in relationship to pre-specified decision criteria defined by ranges of attainable conditional power values. Only an increase in sample size is possible under this approach when observed conditional power falls within the 'promising zone' as described below (Bhatt 2016, Chen 2004, Cui 1999, Mehta and Pocock 2011, Orloff 2009).

The independent statistician will review the conditional power, and make a recommendation per pre-specified criteria about the sample size increasing or maintaining the originally planned sample size.

The sponsor is not allowed to access the interim results prior to the primary analysis.

### **8.12.1 Conditional Power**

Conditional power refers to the probability of concluding a positive study at the end of trial, given interim results of treatment effect and the assumed true treatment effect. The conditional power at the interim analysis  $CP_{\hat{\delta}_1}(z_1, \tilde{n}_2)$  can be defined by the following equation from Mehta and Pocock (2011):

$$CP_{\hat{\delta}_1}(z_1, \tilde{n}_2) = 1 - \Phi\left(\frac{z_\alpha \sqrt{n_2} - z_1 \sqrt{n_1}}{\sqrt{\tilde{n}_2}} - \frac{z_1 \sqrt{\tilde{n}_2}}{\sqrt{n_1}}\right)$$

Where  $\tilde{n}_2 = n_2 - n_1$ ,  $z_\alpha = \Phi^{-1}(1 - \alpha)$ , and  $z_1$  is the value of test statistic as computed at the interim analysis and  $Z_1 = \frac{P_1 - P_0}{\sqrt{P_0 \times (1 - P_0)/n_1}}$ . Define the observed interim estimate,  $\hat{\delta}_1 = \hat{p}_1 - p_0$ , where  $\hat{p}_1$  is Technical Efficacy Rate observed at interim analysis and  $p_0$  is the PG.

Our targeted conditional power at the first interim review is 0.80 (i.e., same as the study power), and we pre-specify a range of conditional power values below 0.80 that would deem our interim results promising and warrant a sample size re-estimation. The “promising zone” for conditional power was defined as between 0.387 and 0.80, as per Mehta and Pocock (2011) method using one-sided alpha of 0.025 and power of 0.80. We propose the following criteria for sample size increase, depending on the zone into which  $CP_{\hat{\delta}_1}(z_1, \tilde{n}_2')$  falls at the interim look.

- Favorable zone: If  $CP \geq 0.8$  (or equivalently  $z_1 \geq 1.806$ ), continue to  $n_2 = 108$
- Promising zone: If  $0.387 \leq CP < 0.8$  (or equivalently  $1.243 \leq z_1 < 1.806$ ) increase sample size to  $n_2^* = \min(n_2', n_{max})$ , where  $n_2'$  is such that  $CP = 0.8$
- Unfavorable zone: If  $CP < 0.387$  (or equivalently  $z_1 < 1.243$ ), continue to  $n_2 = 108$

The following table provide the parameters used for the sample size re-estimation.

Design parameters	Value
Interim Sample Size, $n_1$	54
Cumulative Final Sample Size, $n_2$	108
Incremental Sample Size, $\tilde{n}_2$	54
Pre-specified Maximum Allowable Sample Size, $n_{max}$	180
Drop-out rate	10%
Significance Level (Alpha)	0.025 (one-sided)
Re-Estimated Cumulative Final Sample Size, $n_2^*$	Derived below
Re-Estimated Incremental Sample Size, $\tilde{n}_2'$	Derived below

The re-estimated cumulative final sample size ( $n_2^*$ ) is computed as follows:

$n_2^* = \min(n_2', n_{max})$ , where  $\tilde{n}_2'$  satisfies the condition  $CP_{\hat{\delta}_1}(z_1, \tilde{n}_2') = 1 - \beta$ ,  $\beta = 20\%$  , and  $n_2'$  is the estimated new sample size computed as  $n_1 + \tilde{n}_2'$ .

Based on Mehta and Pocock (2011), this condition is satisfied by the function:

$$\tilde{n}'_2 = \left[ \frac{n_1}{z_1^2} \right] \left[ \frac{z_\alpha \sqrt{n_2} - z_1 \sqrt{n_1}}{\sqrt{n_2 - n_1}} + z_\beta \right]^2, \text{ where } z_\alpha = \Phi^{-1}(1 - \alpha), z_\beta = \Phi^{-1}(1 - \beta), \text{ and } z_1 \text{ is the test statistics as computed at the interim analysis of } n_1 = 54 \text{ evaluable subjects.}$$

Details of  $\hat{p}_1$ ,  $z_1$ , CP, Re-Estimated Incremental Sample Size, Re-Estimated Cumulative Final Sample Size

$\hat{p}_1$	$z_1$ at interim	CP	$\tilde{n}'_2$	$n^*_2$
0.868	1.243	0.387	197	180

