## 7 Sample Size Calculation

This study plans to enroll 120 subjects plus run-in subjects (each site will enroll 2 run-in subjects). The sample size calculation is justified as follows:

The study sample size is determined by hypothesis testing for the comparison of the primary endpoint versus the performance goal (PG). The study's PG is set as 80%. The primary hypothesis test of the primary endpoint is:  $H_0: P \leq P_0$  (80%) vs.  $H_1: P > 80\%$ , where  $P$  is the actual Technical Efficacy Rate of the Neuwave Certus Microwave Ablation System. A sample size of 120 subjects is necessary to achieve at least 80% power for demonstrating that the Technical Efficacy rate of the NeuWave Certus Microwave Ablation System is  $> 80\%$  when the expected performance is 90% and a one-sided significance level of 0.025 is used with the Normal Approximation to the Binomial distribution (Z-test that uses  $S(P_0)$  to estimate the standard deviation), with adjustment for up to 10% dropout.

Each site will enroll 2 subjects first in the run-in phase. So the total sample size will be 120 subjects plus run-in subjects (each site will enroll 2 run-in subjects).

Of the 120 non run-in sample, the number of cases for either disease type is limited at up to 75% (i.e., in the 120 non run-in sample, up to 90 subjects could be NSCLC or oligometastatic lung tumor).

In addition, given the lack of available clinical data for the evaluation of the performance of the investigational product in pulmonary tumor ablation procedures, an adaptive approach will be used to re-estimate the sample size as per the "promising zone" method of Mehta and Pocock (2011) after 50% of the target enrolled subjects complete the Visit 3 Technical Efficacy Evaluation. This procedure involves evaluation of the conditional power (CP) in the interim analysis. If the CP is to fall in the pre-specified "promising zone", the sample size will

be increased to boost the CP up to the target level of 80% for the primary effectiveness endpoint, in the meanwhile, the new sample size will be subject to a predefined maximum value (200 enrolled subjects). If the CP is to fall out of the pre-specified “promising zone”, the study will maintain the originally planned sample size, i.e. 120 subjects plus run-in subjects. For details in sample size re-estimation method, please refer to Section 8.12.

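### Do the printed z1 cut-offs (1.243, 1.806) conflict with the conditional-power zones if more than 54 subjects are evaluable at the interim?

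*SAP*

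**What the plan says.** SAP 8.12.1 sets three zones on the conditional power (CP) scale. The promising zone "for conditional power was defined as between 0.387 and 0.80", and the rule is introduced this way: "We propose the following criteria for sample size increase, depending on the zone into which" CP falls. Each zone also carries, in parentheses, a z1 range described as equivalent; for the promising zone it is "1.243 \leq z_1 < 1.806". The favorable and unfavorable zones keep the final size at n2 = 108. The promising zone raises it to the size that gives CP = 0.80, capped at 180 evaluable.

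The table below the zones opens with "The following table provide the parameters used for the sample size re-estimation" and lists n1 = 54, n2 = 108 and an increment of 54. In the formula for the new increment, z1 "is the test statistics as computed at the interim analysis of" 54 evaluable subjects.

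On timing, SAP 8.12 says the interim "will be performed after 50% of the target enrolled subjects complete the Visit 3 (at least" 54 evaluable). On the deciding quantity, SAP 8.12 says "The sample size re-estimation method is based on evaluation of conditional power in relationship to pre-specified decision criteria", and adds that the independent statistician reviews the CP. SAP 7 words the trigger for an increase in the same terms: "If the CP is to fall in the pre-specified" promising zone.

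**The concern.** CP depends on z1, n1 and n2, so a fixed z1 cut-off can stand for a fixed CP cut-off only at a given information fraction n1/n2. The zone list calls the two scales equivalent without repeating the values of n1 and n2 behind that statement. SAP 8.12 makes 54 a floor. Half of the 120 target subjects is 60, so n1 could be anywhere from 54 to 60 if the interim is taken on those 60.

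If n1 exceeds 54 and n2 stays at 108, one interim result could be promising on one scale and unfavorable on the other. The final size would then be 180 or 108 evaluable (200 or 120 enrolled), depending on which line of the zone list is applied. Such a choice should not be left open until the interim data are known.

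**Working it through.** **Inputs.** One-sided alpha 0.025 (z_alpha = 1.960), target CP 0.80 (z_beta = 0.8416), n1 = 54, n2 = 108 and cap 180 (SAP 8.12.1); P0 = 0.80 and 120 enrolled (SAP 7); 10% dropout at Visit 3 (Protocol 8.2.4). The expected rate of 90% is the planning value in SAP 7.

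**Formulas (SAP 8.12.1).**
- z1 = (p1 − 0.80) / √(0.16/n1)
- CP = 1 − Φ[(z_alpha√n2 − z1√n1)/√(n2 − n1) − z1√(n2 − n1)/√n1]
- new increment = (n1/z1²) × [(z_alpha√n2 − z1√n1)/√(n2 − n1) + z_beta]²

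**1. The plan's own figures.** At n1 = 54, n2 = 108, z1 = 1.243 gives CP = 0.3875 and an increment of 196.4, rounded up to 197; 54 + 197 = 251 is capped at 180. z1 = 1.806 gives CP = 0.7996. The printed row and both cut-offs reproduce. No attainable count at n1 = 54 is classified differently on the two scales: 46/54 is unfavorable, 47/54 and 48/54 promising, 49/54 favorable.

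**2. Larger n1 with n2 held at 108.** The z1 values that match CP 0.387 and 0.80 are:

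| n1 | CP 0.387 | CP 0.80 |
|---|---|---|
| 54 | 1.242 | 1.807 |
| 56 | 1.268 | 1.832 |
| 58 | 1.293 | 1.856 |
| 60 | 1.318 | 1.879 |

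A check of every count for n1 = 54 to 60 finds two disagreements.
- 52/60: z1 = 0.0667/√(0.16/60) = 1.291, promising by z1. The increment is 196.8, so the size is capped at 180. CP = 1 − Φ(1.497 − 1.155) = 0.366, unfavorable, so 108.
- 52/58: z1 = 1.838, favorable by z1, so 108. CP = 1 − Φ(0.901 − 1.707) = 0.790, promising. The increment is 52.1, rounded up to 53, so 58 + 53 = 111.

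**3. The role of n2 = 108.** SAP 7 states the fallback as 120 enrolled. After 60 of 60 evaluable, a final 108 means 48 of the other 60, a 20% loss against the planned 10%. Applying 10% to the remaining 60 gives n2 = n1 + 54.
- 52/60 with n2 = 114: CP = 1 − Φ(1.487 − 1.225) = 0.397, promising, in agreement with z1.
- 52/58 with n2 = 112: CP = 1 − Φ(0.918 − 1.774) = 0.804, favorable, in agreement with z1.

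For n1 = 54 to 60 there is no disagreement with n2 = n1 + 54. With n2 = 2 × n1 the matching cut-offs are again 1.242 and 1.807, because only the ratio n1/n2 matters, and again no count disagrees.

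**4. Consequence, with n2 held at 108.** These are exact binomial sums over all interim counts, with the null-variance Z-test at the end (at least 95/108 or 155/180 needed).

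| n1 | Scale | Power at 90% | Mean evaluable at 90% | Type I error at 80% |
|---|---|---|---|---|
| 60 | z1 | 0.861 | 121.9 | 0.0203 |
| 60 | CP | 0.829 | 114.2 | 0.0202 |
| 58 | z1 | 0.835 | 116.6 | 0.0199 |
| 58 | CP | 0.829 | 117.2 | 0.0187 |

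**5. How often.** If each of 60 subjects is evaluable with probability 0.90, P(n1 = 60) = 0.90^60 = 0.0018. At a true 90%, P(52/60) = 0.107. The product is 0.0002, or 0.02%. If the evaluable probability were 0.95, 0.98, 0.99 or 1.00 (assumed values), the chance would be 0.5%, 3%, 6% or 11%.

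**The case for a change.** The best argument for a change is that SAP 7 times the re-estimation by completion of the Visit 3 efficacy evaluation. A subject who has completed that evaluation will usually be evaluable, so much of the 10% dropout may already have been removed and n1 close to 60 is a natural reading. On that reading 52/60 is no rarity: 11% if all 60 are evaluable and the true rate is 90%. The stake in that case is also real. From 52/60 at a true 90%, the chance of final success is about 0.65 at 108 and 0.95 at 180. The statistician would be choosing between two printed criteria with the data in hand, and one sentence in advance would prevent it.

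Much of this stands as description. The plan has no sentence on n1 above 54, and a literal n2 = 108 does produce the 52/60 split. What does not stand is that the plan leaves the choice open. CP is named as the criterion in SAP 7, in SAP 8.12 and in the sentence that introduces the zones. The z1 ranges appear only in parentheses, beside a table fixed at n1 = 54 and n2 = 108. The added sentence would only restate that precedence. It would not gain power either: at n1 = 60 with n2 = 108, CP gives 0.829 and the z1 cut-offs 0.861. Restricting the interim to the first 54 evaluable subjects would also remove the split, but would leave up to 6 evaluable subjects out of it.

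**Conclusion.** The concern does not call for a change. The cut-offs are correctly calculated for the design parameters printed beside them, and more generally whenever n1/n2 = 0.5. For a larger n1 the plan already supplies a deciding quantity, CP, and a formula that accepts the actual n1. This is a gap that the analyst fills by following the text.

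The size is small. With n2 held at 108 and n1 between 54 and 60, two counts are affected, and one of them moves the final size by three subjects. The other needs all 60 subjects evaluable followed by a 20% loss in the second half. Type I error stays below 0.025 and power above the planned 80% on either scale.

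This rests on three assumptions: n1 does not exceed 60, although the plan sets no upper limit; each evaluable subject contributes one independent result; and the final test is the null-variance Z-test. Fixed n2 values other than 108 can produce isolated splits of the same kind (for example 51/57 with n2 of 118 to 120), and CP settles those in the same way.

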### 8.13 Plans for Primary and Final Analysis

Primary analysis will occur after all enrolled subjects finish the 1-month visit, aiming to evaluate Technical Efficacy Rate, and periprocedural endpoints during the 1st month after initial lung tumor ablation. If the primary effectiveness endpoint success criteria is met, the study is considered as a success and the study report will be submitted to NMPA for the registration application. Per the imputation rule for the sensitivity analysis of the primary endpoint, if the subject does not have a Visit 3, then chest enhanced CT at Visit 4 will be sent to the IRC for local tumor progression assessment, and the primary effectiveness endpoint at Visit 3 will be imputed per if local tumor progression occurs by Visit 4. Therefore, if there is any imputation that requires the evaluation from Visit 4, the primary analysis will occur after these subjects' visit-4 results are ready or confirmed as missing.

A final analysis will be performed after all subjects have completed the study or early discontinued from the study.

### 8.14 Handling of Missing Data

For missing data, the number of missing be displayed. All summaries will be performed only on subjects undergoing ablation with the NeuWave Certus Microwave Ablation System. A new subject will be recruited to replace any subject who discontinues the ablation procedure after the ablation probe punctures the skin and before the microwave energy is initiated. If an initial ablated tumor is re-ablated before the Visit 3 Technical Efficacy assessment, the re-ablated tumor will be considered as a failure.

- In the primary analysis of the primary efficacy endpoint: other subjects with missing primary efficacy data or other early discontinuations will not have data imputation.
- In the sensitivity analysis of the primary efficacy endpoint: as a conservative surrogate endpoint, if the subject does not complete Visit 3, then chest enhanced CT at Visit 4 will be sent to the IRC for local tumor progression assessment, and if local tumor progression occurs, the primary efficacy endpoint at Visit 3 will be imputed as a failure.

If there is no local tumor progression at Visit 4, the primary efficacy endpoint at Visit 3 will be imputed as a success. If a subject does not have both Visit 3 and Visit 4, the subject will be excluded from the analysis of the primary efficacy endpoint.

No imputations will be made for missing demographics, baseline characteristics, tumor characteristics, or secondary and exploratory endpoint variables in the analyses.

For time-to-event analysis, all censored data will be accounted for using appropriate statistical methods as described in sections 8.10.4-8.10.6.

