3.2. Contents of Clinical Trial

This study employs single-arm, prospective and multi-center design with single-arm performance goal comparing study device performance indexes with the predetermined performance goal, in order to evaluate study device efficacy and safety. Approximately 120 plus run-in subjects (each site will enroll 2 run-in subjects) of Chinese patients with non-small cell lung cancer or oligometastatic lung tumor scheduled for microwave ablation will be recruited. After the informed consent is signed, lung cancer patients according to the inclusion and exclusion criteria will be included in this study. All qualified subjects at the study sites will receive the same procedure: microwave ablation using only the NeuWave Certus Microwave Ablation System and accessories. Subjects in this study will come to their study site for the ablation procedure. After the ablation procedure, the patient will be observed according to medical routine, and afterwards may return home. If the Study Doctor decides it is warranted for patient safety, the patient will remain in the hospital longer. All subjects will be required to return to their study site for at least 4 follow-up visits over a period of 12 months to assess the efficacy and safety of ablation.

Computerized tomography (CT) is used to evaluate the efficacy to verify whether patient's lung tumor is completely ablated. CT scan will be carried out approximately 10 minutes after the ablation to assess Technical Success Rate and A0 Ablation Rate. Enhanced CT scan will be completed within 30 days (± 7 days) after the ablation to evaluate Technical Efficacy Rate. During the subsequent visits in Months 3, 6, and 12 after the ablation, subjects will receive at least one enhanced CT scan each time at the study site to observe whether there are imaging manifestations of tumor progression inside the ablation zone and at its margin. These enhanced CT scans will serve as the basis for determining the Local Tumor Progression. Progression-Free Survival including local, regional, or distant progression will also be determined according to the study physician and/or the patient's treating oncologist. Another valuable endpoint during the 12-month follow-up period will be overall survival.

Within 30 days after the ablation (initial or repeated), all adverse events (AE) and serious adverse events (SAE) experienced by the patient will be evaluated; from 30 days after the ablation to the

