8.4. Criteria and Reason for Terminating the Trial Based on the Statistical Results

There is no planned termination of the trial due to statistical reasons.

8.5. Statistical Method of All Data, together with the Handling Method of Missing, Unused and Error Data (including Termination and Withdrawal Halfway) and Unreasonable Data

All effectiveness endpoint analyses will be performed only on subjects undergoing ablation with the NeuWave Microwave Ablation System and observed data will be analyzed.

1) In the primary analysis of the primary effectiveness endpoint:

- A new subject will be recruited to replace any subject who discontinues the ablation procedure after the ablation probe punctures the skin and before the microwave energy is released.
- If an initial ablated tumor had re-ablation before the Visit 3 Technical Efficacy assessment, the re-ablated tumor will be considered as failure.
- Other subjects with missing parameters or other early discontinuations will not have data imputation.

2) A sensitivity analyses will also be performed for the primary effectiveness endpoint after missing data are imputed according to the following methods:

- A new subject will be recruited to replace any subject who discontinues the ablation procedure after the ablation needle punctures the skin and before the microwave energy is released.
- If an initial ablated tumor had re-ablation before the Visit 3 Technical Efficacy assessment, the re-ablated tumor will be considered as failure.
- As a conservative surrogate endpoint, if the subject does not have Visit 3, then chest enhanced

CT at Visit 4 will be sent to the IRC for local tumor progression assessment, and if local tumor progression occurs, the primary effectiveness endpoint at Visit 3 will be imputed as a failure. If there is no local tumor progression at Visit 4, the primary effectiveness endpoint at Visit 3 will be imputed as successful. If a subject does not have both Visit 3 and Visit 4, the subject will be excluded from the analysis of the primary effectiveness endpoint.

For secondary endpoint missing value, there will be no imputation. The handling methods for missing values and outliers are detailed in the Statistical Analysis Plan (SAP).

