## **8.9 Primary Endpoint and Associated Hypotheses**

Analyses will be conducted on the FAS, PPS, and run-in set.

The primary efficacy endpoint is Technical Efficacy Rate, defined as the percentage of tumors that are completely covered by the ablation area without signs of pathological enhancement as assessed by lung enhanced CT at Visit 3 (i.e., 30 days $\pm$ 7 days after the first ablation). Each subject will have a maximum of one NSCLC tumor or a maximum of three ipsilateral oligometastatic lung tumors to be ablated, each of which will be defined as a success or failure. If the initial ablated tumor had re-ablation before Visit 3 Technical Efficacy assessment, the re-ablated tumor will be considered as a failure. The re-ablation will not change or extend the subject's follow-up schedule. Technical Efficacy Rate will be analyzed based on both the target tumor level and subject level.

The Technical Efficacy Rate is assessed by both the study physician (i.e., PI) and Independent Central Imaging Committee (IRC). Primary statistical analysis and hypothesis testing for the primary effectiveness endpoint will be based on IRC's evaluation results. For IRC evaluation, there will be at least two reviewers providing their results. If the two reviewer's results are the same, the first one's result will be used. If the two reviewer's results differ, a third reviewer will evaluate and his or her result will be used for the analysis. This analysis rule will be applied for all IRC-based endpoint.

The null and alternative hypotheses for primary analysis of the primary endpoint are as follows:

$$H_0: P \leq P_0 (80\%)$$

$$H_1: P > 80\%,$$

where P is the actual Technical Efficacy Rate using the NeuWave Certus Microwave Ablation System.

If the initial ablated tumor had re-ablation before the Visit 3 Technical Efficacy assessment, the re-ablated tumor will be considered as a failure. Other tumors with missing parameters or other early discontinuations will not have data imputation.

For multi-target-tumor subjects, his or her largest Target Tumor, determined by the maximum three dimensions of each target tumor, will be used for subject-level analysis conservatively.

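### The sensitivity analysis for missing Visit 3 results replaces Technical Efficacy with absence of local progression at Visit 4, a different criterion, and the label *conservative* is not supported

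*SAP*

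**What the plan says.** SAP 8.9 counts a target tumour as a success if it is "completely covered by the ablation area without signs of pathological enhancement as assessed by lung enhanced CT at Visit 3". In the primary analysis a missing result is not imputed. SAP 8.9 names two sensitivity analyses: a repeat on the per-protocol set, and a repeat on the full analysis set with the imputation rule of SAP 8.14.

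That rule opens: "as a conservative surrogate endpoint, if the subject does not complete Visit 3, then chest enhanced CT at Visit 4 will be sent to the". The recipient is the review committee, which is to assess the scan for local tumour progression. Progression is imputed as failure. Otherwise, "If there is no local tumor progression at Visit 4, the primary efficacy endpoint at Visit 3 will be imputed as a success". Protocol 8.5 agrees: "If there is no local tumor progression at Visit 4, the primary effectiveness endpoint at Visit 3 will be imputed as successful". SAP 8.13 repeats the rule and holds back the primary analysis until these Visit 4 results are available or confirmed missing. Where both visits are absent there is no imputation: "If a subject does not have both Visit 3 and Visit 4, the subject will be excluded".

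On repeat treatment, SAP 8.14 says, ahead of both analyses: "If an initial ablated tumor is re-ablated before the Visit 3 Technical Efficacy assessment, the re-ablated tumor will be considered as a failure". Protocol 8.5 lists the same rule inside the sensitivity analysis.

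On local progression, Protocol 3.2 says that the CTs at months 3, 6 and 12 serve to "observe whether there are imaging manifestations of tumor progression inside the ablation zone and at its margin". Protocol 7.1.6 leaves the detailed endpoint definitions to a separate imaging chapter, which is not among the documents.

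**The concern.** Technical Efficacy is a statement about completeness at about day 30. Local progression, as Protocol 3.2 describes it, is a statement about what has developed since. A tumour with residual disease that has not progressed by month 3 fails the first and passes the second. The rule does not ask the IRC to read coverage or enhancement at Visit 4, and it makes no use of the classification on the day of ablation.

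Of the two sensitivity analyses, only this one deals with missing Visit 3 results, and Protocol 8.2.4 expects 10% of subjects to be missing at that visit. If the substitute measures something else, its agreement with the primary result says little about whether the missing data matter. Calling it *conservative* invites more reassurance than it can give.

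**Working it through.** **1. The plan's own figure.** Inputs from SAP 7: P0 = 0.80, P1 = 0.90, one-sided alpha 0.025, power 80%, dropout 10%, Z-test with the standard deviation taken at P0.

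n = [1.960·√(0.8·0.2) + 0.842·√(0.9·0.1)]² / 0.10² = 107.4, so 108 evaluable; 108/0.9 = 120 enrolled.

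The stated 120 is reproduced (power at 108 is 80.3%). The planned number missing is 120 − 108 = 12.

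**2. The two criteria side by side.**

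| True Visit 3 state | Visit 4 reading | Imputed | Error |
|---|---|---|---|
| Complete, no enhancement | No progression | Success | None |
| Complete, no enhancement | Progression | Failure | Too strict (recurred after Visit 3) |
| Incomplete or enhancing | Progression | Failure | None |
| Incomplete or enhancing | No progression | Success | Too lenient |

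The number of successes is overstated by (row 4 minus row 2). A conservative rule needs row 2 to be at least as large as row 4. The documents give a figure for neither.

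**3. Can row 4 occur under this protocol?** Three provisions together say yes.
- Protocol 7.2.3 (Visit 2A) classes as A2 an ablation that could not be completed once power had started.
- The same section keeps every screened tumour that received power as a target tumour, so an A2 tumour stays in the analysis.
- Protocol 7.2.3 (unscheduled visits) lists residual tumour and local progression as separate reasons for re-ablation, so the protocol treats them as different states.

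An A2 tumour whose subject misses Visit 3 and shows no progression at Visit 4 is therefore imputed as a success, subject to what the imaging chapter says.

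**4. Size.** z = (x/n − 0.8)/√(0.16/n), with a pass if z > 1.96. This is equivalent to the SAP 8.9 lower limit exceeding 0.8 while the proportion is not above 90%, which holds for every row below. Assumptions: one tumour per subject, 12 missing, all 12 with a Visit 4 CT.

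| Case | x/n | z | Lower limit | Result |
|---|---|---|---|---|
| Observed | 94/108 | 1.83 | 0.795 | Fail |
| All 12 imputed as success | 106/120 | 2.28 | 0.812 | Pass |
| Two of the 12 correctly scored as failure | 104/120 | 1.83 | 0.795 | Fail |
| Observed, narrowest pass | 95/108 | 2.07 | 0.804 | Pass |
| All 12 imputed as success | 107/120 | 2.51 | 0.820 | Pass |
| Minimum pass at 120 | 105/120 | 2.05 | 0.803 | Pass |

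From 95/108, two misclassified tumours are tolerated (107 − 2 = 105, pass) and three are not (104, fail).

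**5. If fewer return for Visit 4.** From 94/108 with r imputed successes:
- r = 3: 97/111 = 0.8739; z = 0.0739/0.0380 = 1.95, fail.
- r = 4: 98/112 = 0.8750; z = 0.0750/0.0378 = 1.98, pass.

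Four returning subjects, all imputed as successes, are enough to move this example across the line.

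**6. When does the rule lower the estimate?** With s successes in n observed and a fraction q of the imputed tumours progressing, the rate falls only if q > 1 − s/n. At 94/108 that is q > 14/108 = 13.0%. For orientation only, the colorectal-metastasis series in Protocol 4.2 had 10% local progression over a median of 25.6 months and 90% Technical Efficacy at first treatment. Its definitions may differ from this trial's, but it gives no reason to expect three-month progression to exceed the Visit 3 failure rate.

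**The case against.** Several points on the other side stand.

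- **The rule can err strictly.** A reader might infer that changing the criterion can only lower the bar. That would be so at a fixed time, but the reading also moves from 30 ± 7 days to 3 months ± 14 days. A tumour clean at Visit 3 that recurs by Visit 4 is imputed as a failure. This may be what *conservative* was meant to convey; it makes the direction uncertain, and does not make the rule conservative.
- **The IRC definition is not in hand.** Note 21 to the Schedule of Activities describes the follow-up reading in terms of malignant lesions at the ablation site, which could include residual tumour. Without a Visit 3 scan the IRC also has no scheduled earlier post-ablation contrast CT from which to call enhancement stable. If the imaging chapter counts residual enhancement as progression, the gap narrows.
- **Re-ablated tumours are largely covered.** A reader might infer that tumours already re-ablated are scored as successes. Re-ablation before the Visit 3 assessment is a failure in this analysis too. The only open case is a tumour re-ablated before Visit 4 when no Visit 3 assessment ever took place. Even there, the wording can fairly be read as failure.
- **The trigger is ambiguous, not wrong.** The contrast CT is a listed Visit 3 procedure, so a subject without a usable one arguably did not complete the visit.
- **The illustration is an upper bound.** Some drop-outs will not return for Visit 4 and are then excluded. From 95/108, three failures among 12 are needed to matter; at a 10% failure rate the chance of three or more is about 11%, and at 12% about 17%, even if none of them progresses by Visit 4.

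**Conclusion.** The point holds as a mismatch of criterion in a supportive analysis. The endpoint requires complete coverage and no pathological enhancement; the imputation requires only no local progression two months later. An incompletely ablated tumour, including one classed A2 on day 0, can be imputed as a success, and a late recurrence can be imputed as a failure. The net direction is not fixed, so *conservative* is unsupported.

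At the planned 10% missing, with all 12 having a Visit 4 CT and one tumour each, the rule can take 94/108 (fail) to 106/120 (pass), and two misclassified tumours reverse that. Tumour-level counts with several tumours per subject would differ. The conclusion also depends on the imaging chapter not already counting residual enhancement as progression.

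It does not follow that the trial could be declared a success through this rule. SAP 8.9 makes the complete-case analysis on the full analysis set the primary one, and a sensitivity analysis cannot rescue a failed primary result. What is weakened is the only check on missing Visit 3 data. It should be corrected, but it does not undermine the primary test.

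**What to change.** In SAP 8.14, SAP 8.13 and Protocol 8.5:

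1. Have the IRC read the Visit 4 contrast CT with the Technical Efficacy criterion. Impute failure if there is residual or pathological enhancement, incomplete coverage or local progression; otherwise impute success.
2. State that a tumour re-ablated before the substitute CT, when no Visit 3 assessment took place, is scored as a failure.
3. Word the trigger as no evaluable Visit 3 contrast CT.
4. Delete *conservative*.

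Cost: wording in the SAP, the protocol and the imaging chapter, and a changed question on the read form. The scan and the readers stay the same. The imaging chapter must say how coverage is judged at three months, since the documents describe coverage readings only for the CT about 10 minutes after ablation and the Visit 3 CT. The sensitivity estimate may be slightly lower. Subjects missing both visits remain excluded, so this change aligns the check with the endpoint but does not address them.
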